- Cohort 4 (N=Approximately 30 [10 initial/up to 20 expansion]): (Two times weekly dosing) VP-315 once-daily dosing of 8 mg, administered on 2 consecutive days in one week (W1D1, W1D2). The planned dosing regimen will be a split dose of VP-315 for all treatments. The 500μL (8 mg) dose will be divided into 2 injections given at least 15 minutes and no more than 30 minutes apart, with 30% (150 μL) administered in the first injection and the remaining 70% (350 μL) with the second injection. Treatment for a second Target Lesion may begin on D1 of the next week (W2D1, W2D2). Each individual target lesion is treated for the assigned 2 days only (regardless of necrosis status). Up to 2 target lesions may be treated up to 4 total doses.
- Cohort 5 (N=Approximately 30 [10 initial/up to 20 expansion]): (Three times weekly dosing) VP-315 once-daily dosing of 8 mg, administered on 3 consecutive days in one week (W1D1, W1D2, W1D3). The planned dosing regimen will be a split dose of VP-315 for all treatments. The 500μL (8 mg) dose will be divided into 2 injections given at least 15 minutes and no more than 30 minutes apart, with 30% (150 μL) administered in the first injection and the remaining 70% (350 μL) with the second injection. Treatment for a second target lesion may begin on D1 of the next week (W2D1, W2D2, W2D3). Each individual target lesion is treated for the assigned 3 days only (regardless of necrosis status). Up to 2 target lesions may be treated up to 6 total doses.

See (Table 7-1)

In Part 1 of the study, each 7-day treatment week comprises up to 3 consecutive treatment days followed by a no-treatment period of at least 4 days. In Part 2 of the study, each 7-day

treatment week comprises up to 2 or 3 consecutive treatment days followed by a no-treatment period of at least 4 days. Dosing will commence in a single target lesion. In Part 1 and Part 2 Cohorts 1 and 2, once a target lesion has necrosed, treatment of that lesion stops, and treatment of a subsequent target lesion (up to 2 total, including the original target lesion) may continue on Day 1 of the following week. In Part 2 Cohorts 4 and 5, treatment of a second target lesion begins on W2D1 (not based on status of necrosis of target lesion 1).

For the first 10 subjects enrolled into Cohorts 4 and 5: after each treatment, subjects will remain in the study center for up to 2-hours post second injection for safety monitoring (e.g., continuousblood pressure, electrocardiographic and AE monitoring).

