# 7.3.2 VP-315 Dosing Strategy

## **7.3.2.1** Study Part 1

In Part 1 of the study, the starting total daily dose for the evaluation of VP-315 will be 2 mg for the first subject. Subjects will receive ascending once-daily doses (increasing in 1-mg increments for up to 3 days in a 7-day treatment week [≥4 days off between treatment weeks]) until the first lesion is necrosed or until the subject experiences a DLT, whichever occurs first (Figure 7-2). Subjects will be observed for DLTs throughout the treatment period during Part 1.

After receiving a dose, the subject will return to the clinic the following day for assessment by the investigator. If, in the opinion of the SRC (see Section 7.4), there has been no DLT and if the lesion is not necrotic, the dose will be escalated, and the same lesion will continue to be treated before any additional target BCC lesions may be treated.

When a target lesion is deemed necrotic in the opinion of the SRC, the subject will not receive any additional treatment for that lesion, and a safety assessment visit will be performed instead. If the subject has additional lesions and no DLT has occurred, treatment of the next lesion may begin on day 1 (D1) of the next week. A maximum of 2 target BCC lesions may be treated, and only 1 lesion may be treated at a time. Subjects will be treated for a maximum of 2 weeks and a maximum total daily dose of 8 mg.

The starting dose will be escalated between subject cohorts in 1-mg increments after the previous cohort has completed Week 1 dosing (the DLT observation period) (Table 7-1). Dose escalation in Part 1 will end when 2 subjects experience a DLT at the same nominal dose (indicating that the preliminary MTD has been exceeded, and the preliminary MTD is the dose immediately below where any DLT occurred) or until a maximum VP-315 total daily dose of 8 mg is reached in up to 6 subjects.

## 7.3.2.2 Study Part 2

Part 2 will be initiated upon completion of Part 1 to determine the optimal dosing regimen of VP-315. There were no DLTs observed in Part 1 of the study and the maximum dose of 8 mg was achieved. Therefore, the dose to be evaluated in Part 2 will be a total daily dose of 8 mg in the following 5 Cohorts:

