- Cohort 5 (N= Approximately 30 (10 initial/up to 20 expansion): (Three times weekly dosing) VP-315 once-daily dosing of 8 mg, administered 3 consecutive days in one week (W1D1, W1D2, W1D3. The planned dosing regimen will be a split dose of VP-

315 for all treatments. The  $500\mu L$  (8 mg) dose will be divided into 2 injections given at least 15 minutes and no more than 30 minutes apart, with 30% (150  $\mu L$ ) administered in the first injection and the remaining 70% (350  $\mu L$ ) with the second injection. Treatment for a second target lesion may begin on D1 of the next week (W2D1, W2D2). Each individual target lesion is treated for the assigned 3 days only (regardless of necrosis status). Up to 2 target lesions may be treated – **up to 6 total doses.** 

After receiving a dose, the subject will return to the clinic the following day for assessment by the investigator. If, in the opinion of the Medical Monitor, the lesion is not necrotic Cohorts 1 and 2 only, the same lesion will continue to be treated before any additional target BCC lesions are treated. When a lesion is deemed necrotic in the opinion of the Medical Monitor, the subject will not receive any additional treatment for that lesion.

- If the subject has additional lesions, treatment of the next lesion may begin on D1 of the next week. A maximum of 2 target BCC lesions may be treated, and only 1 lesion may be treated at a time.
- Subjects in Cohorts 4 and 5 with only 1 target lesion that complete week one of treatment and the W1 safety assessment visit without complete necrosis should return for a Limited Safety Assessment Visit on W2D1 for further evaluation of the lesion for necrosis. No additional treatment will be provided.
- Subjects in Part 2 (all Cohorts) that complete week two of treatment and the W2 Safety Assessment Visit without complete necrosis should return for a Limited Safety Assessment visit on W3D1 for further evaluation of the lesion for necrosis. No additional treatment will be provided.

For the first 10 subjects enrolled into Cohorts 4 and 5: after each treatment, subjects will remain in the study center for up to 2 hours post second injection for safety monitoring (e.g., continuous blood pressure, electrocardiographic and AE monitoring).

Following the final treatment of the 10th subject in Cohort 4, enrollment into Cohort 5 may be initiated for 10 subjects.

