**Table 7-1 Dose Regimen (Part 2 Cohorts 1-5)** 

#### CRO must be contacted for each subject before treatment to confirm Cohort assignment

Cohorts	W1D1	W1D2	W1D3	W1D4	W2D1	W2D2	W2D3	W2D4*		
	4 mg loading	8 mg	8 mg	Safety	8 mg	8 mg	8 mg	Safety		
Cohort 1 –										
loading dose (N=3 to 6)	If 1 TRAE SI occurs in the first 3 subjects, enroll up to 6 subjects									
(* * 5 55 5)	— If no further TRAEs SI occur, then begin enrollment into Cohort 2									
	- If	2 TRAEs SI occi	ur in 6 subjects, the	en begin enrollment	into Cohort 3					
	W1D1	W1D2	W1D3	W1D4	W2D1	W2D2	W2D3	W2D4		
Cohort 2 – No	8 mg	8 mg	8 mg	Safety	8 mg	8 mg	8 mg	Safety		
loading dose (N=3 to 6)										
	• If 1 TRAE SI occurs in the first 3 subjects, begin enrollment into Cohort 4 with 30/70 split dosing of 8mg for each treatment									
Cohort 3 – has been removed										

NOTE: Cohorts 1-2: Treatment continues until TRAE (includes TRAE SI) or significant necrosis of Target Lesion #1 as determined by Sub-SRC. If significant necrosis is determined, the current assessment is changed to an assessment-only visit, and no VP-315 is administered for the remaining days of the current Treatment Interval/Week. If the subject has an additional target lesion and a TRAE has not occurred, treatment of Target Lesion #2 may begin at D1W2 of next Treatment Interval/Week. Up to 2 target lesions may be treated. Subjects that complete two weeks of treatment and the W2D4 Safety Assessment Visit without achieving complete necrosis, should return for a Limited Safety Assessment Visit on W3D1 for further evaluation of the lesion for necrosis.

Cohort 4		Lesio	n #1 Treatmei	nt	Lesion #2 Treatment						
2-day dosing regimen	W1D1	W1D2	W1D3	W2D1		W2D1	W2D2	W2D	3	W3D1	
N=30	20/70 9	20/70 9	S a fator	I ''4. J C. C.4.		20/70 9	20/70 9	Safa4		Limited	
(10 initial/ 20 expansion)	30/70 8 mg	30/70 8 mg	Safety Limited Safety		30/70 8 mg	30/70 8 mg	g Safet	y	Safety		
Cohort 5		Lesio	n #1 Treatmer	nt		Lesion #2 Treatment					
3-day dosing regimen	W1D1	W1D2	W1D3	W1D4	W2D1	W2D1	W2D2	W2D3	W2D4	W3D1	
N=30 (10 initial/	30/70 8 mg	30/70 8 mg	30/70 8 mg	Safety	Limited Safety	30/70 8 mg	30/70 8	30/70 8 mg	Safety	Limited Safety	
20 expansion)					Salety		mg			Salety	

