#### 7.4.2 Dose Escalation

Subjects may be treated for a maximum of 2 weeks and a maximum total daily dose of 8 mg in all parts of the study (1 and 2).

Details of dose escalation are provided in Section 7.3.2. Determination of whether or not to advance VP-315 doses will be made following safety review by the SRC and Sponsor-appointed Medical Monitor (or designee). The National Cancer Institute (NCI) Common Terminology Criteria for Adverse Events (CTCAE) v5.0 will be used to grade safety events. The safety review will include at a minimum:

- All AEs, including intensity and investigator assessment of drug causality
- Routine laboratory test results (chemistry, hematology) and available serum tryptase findings

- Treatment-emergent changes on electrocardiogram (ECG)
- Treatment-emergent changes on vital signs

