### **5.5. Definition of Baseline and Treatment Groups**

Baseline is defined as the most recent non-missing value obtained prior to first injection of study treatment. Summaries will be provided for the following groups, unless limited to a subset of these groups elsewhere in this SAP:

- Part 1
- Part 2
  - Cohort 1
  - Cohort 2
  - Cohort 4
  - Cohort 4 Expansion
  - Cohort 5
  - Cohort 5 Expansion
  - Overall (i.e., Part 2 Total, Displayed Total, or Expansion Total)

No other group or subgroup analyses will be performed.

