## 8. Efficacy Analysis

The conventions of Section 5 of this SAP will be applied. Tables and figures will be prefixed with 14, and listings will be prefixed 16. Tables will be provided for Part 1 and Part 2 unless noted otherwise.

Each subject can have at most two distinct target lesions (TL1, TL2) and at most three distinct non-target lesions (NTL1, NTL2, NTL3). All subjects are to have TL1, but not every subject will have additional lesions. The efficacy table summaries will be provided by subject lesion.

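### In Part 1 and Cohorts 1-2 a second target lesion is injected only after early necrosis of the first, and the Part 2 Total pools those lesions with Cohort 4-5 second lesions not selected on necrosis

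*Protocol*

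**What the plan says.** **When TL2 is injected, Part 1 and Cohorts 1-2.**
- The synopsis states that "once a target lesion has necrosed, treatment of that lesion stops, and treatment of a subsequent target lesion" may continue on Day 1 of the following week.
- If TL1 is not necrotic, protocol 7.3.2.1 (Part 1) says "the same lesion will continue to be treated before any additional target BCC lesions may be treated". Section 7.3.2.2 says the same for Cohorts 1 and 2: "the same lesion will continue to be treated before any additional target BCC lesions are treated".
- Only one lesion is treated at a time, and protocol 7.4.2 caps the duration: "Subjects may be treated for a maximum of 2 weeks and a maximum total daily dose of 8 mg".
- Toxicity is a second condition. In Part 1 the next lesion requires that no DLT has occurred. For Cohorts 1-2 the note to Table 7-1 reads "If the subject has an additional target lesion and a TRAE has not occurred, treatment of Target Lesion #2 may begin at D1W2".
- SAP 3.1, 3.3 and 3.4 repeat the necrosis condition.

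**When TL2 is injected, Cohorts 4-5.** The synopsis says "treatment of a second target lesion begins on W2D1 (not based on status of necrosis of target lesion 1"), and SAP 3.6 and 3.7 agree that each lesion gets its fixed days regardless of necrosis.

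**How the SAP tabulates it.** Section 8 says "The efficacy table summaries will be provided by subject lesion". Section 5.5 lists Part 1, each Part 2 cohort and "Overall (i.e., Part 2 Total, Displayed Total, or Expansion Total") as the default groups, and rules out other subgroups. Sections 8.1, 8.2 and 8.6 are restricted to treated TL1 and TL2. Section 8.3 covers excised lesions and 8.5 covers lesions by visit, neither with a restriction to treated TL2s. Only 8.6, among the efficacy tables, specifies a total over Cohorts 4 and 5 alone (the Displayed Total).

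**The concern.** The two groups reach a treated TL2 by different routes. In Part 1 and Cohorts 1-2, a subject whose TL1 did not necrose early spends Week 2 on TL1 and contributes no treated TL2. In Cohorts 4-5 such a subject does contribute one.

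If lesions in the same person tend to respond alike, the TL2 rows of Part 1 and Cohorts 1-2 look better than a second lesion would in an unselected subject. The protocol makes some correlation credible: section 2.2.5 describes T-cell expansion in blood and regression of noninjected lesions, and abscopal effect is an endpoint. A reader could take these rows as replication of efficacy in a second lesion, when they are conditional on an early response in the first. The Part 2 Total TL2 row has no single definable population, and in 8.3 it would carry a 95% confidence interval for the mean. The study is descriptive and is meant to inform a pivotal design, so the tables are the result. No SAP footnote or sensitivity analysis addresses this; 8.7 deals with missing end-of-treatment values only.

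**Working it through.** **1. Subject base.** SAP 3.2 gives Part 2 N = 82. The cohorts sum to 6 + 3 + 0 + 36 + 37 = 82, so the figure reproduces. Cohorts 1-2 supply 9 of 82 (11.0%) and Cohorts 4-5 supply 73. Part 1 (N = 10) is outside the Part 2 Total.

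**2. Is the necrosis condition strict?** Treatment lasts two weeks and TL2 starts on a Day 1, so W2D1 is its only possible start. If TL1 necroses during Week 2, the next Day 1 falls in Week 3, beyond the limit. A treated TL2 in Part 1 or Cohorts 1-2 therefore implies that TL1 was judged necrotic in time for W2D1.

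**3. Bias in the selected rows.** Let p be the TL2 clearance rate at excision, q the rate of early TL1 necrosis, and r the correlation between the two within a subject. The documents give none of them. The covariance is r × sqrt[p(1−p)q(1−q)]; dividing by q gives

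P(TL2 clears | TL1 necrosed) − p = r × sqrt[p(1−p)(1−q)/q].

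With p = 0.5:
- q = 0.5: sqrt(0.25 × 1) = 0.50, so r = 0.2 gives 10 points and r = 0.5 gives 25.
- q = 0.8: sqrt(0.25 × 0.25) = 0.25, so 5 and 12.5 points.
- q = 0.3: sqrt(0.25 × 0.7/0.3) = 0.764, so 15.3 and 38.2 points, on fewer lesions.
- r = 0, or q = 1: zero.

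**4. Weight of Cohorts 1-2 in the Part 2 Total TL2 row.** Assume the share of subjects with a second target lesion is equal across cohorts and ignore the toxicity filter. The share then cancels and the weight is w = 9q/(9q + 73). The shift in the total is w times the bias.

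| q | w | shift at r = 0.2 | shift at r = 0.5 |
|---|---|---|---|
| 0.3 | 2.7/75.7 = 3.6% | 0.5 points | 1.4 points |
| 0.5 | 4.5/77.5 = 5.8% | 0.6 points | 1.5 points |
| 0.8 | 7.2/80.2 = 9.0% | 0.4 points | 1.1 points |

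**5. Expected counts.** If 30 of the 73 Cohort 4-5 subjects (41%) have a treated TL2 (assumed) and q = 0.5, Cohorts 1-2 contribute 9 × 0.41 × 0.5 ≈ 1.8 treated TL2s: about 1.2 in Cohort 1 and 0.6 in Cohort 2. Part 1 has about 10 × 0.41 × 0.5 ≈ 2.

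**6. If second lesions are unevenly spread.** Three treated TL2s from Cohorts 1-2 against ten from Cohorts 4-5 would give w = 3/13 = 23%, and a shift of 2.3 to 5.8 points for a bias of 10 to 25 points. This is an outer case, not an expectation.

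**The case against.** The strongest reply is that little depends on this. Each cohort has its own column, Part 1 is outside the Part 2 Total, and SAP section 3 states the TL2 rule for each cohort. SAP 7.1.2 reports TL2 administration and the reasons for non-administration. The four categories in 8.6 already let a reader recover histologic and clinical clearance of TL2 for Cohorts 4-5. With one or two TL2s per selected row, one lesion moves the row by 50 to 100 points, which swamps the bias. No formal inference is planned, and Part 1 efficacy is exploratory. All of this stands and is why the point is minor.

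Four stronger readings are tempting but not supported:
- *All TL2 efficacy rows come from responders.* This is firm only for 8.1, 8.2 and 8.6. The protocol glossary recognises target lesions that were not treated, and SAP 7.1.2 provides for a TL2 not administered. The 8.3 and 8.5 rows may therefore mix injected and uninjected TL2s, and the direction of any bias there is unknown. Protocol 5.4 would instead follow untreated eligible lesions as nontarget, so the text does not settle it.
- *The condition is clearance of TL1.* It is visual necrosis during treatment, judged by the SRC, sub-SRC or Medical Monitor. The endpoints are read at excision, weeks later. The 25-point figure needs q = 0.5; it halves at q = 0.8.
- *Cohorts 1-2 carry their full 11% weight in the TL2 total.* On an equal share of second lesions, that requires q = 1, where there is no selection and no bias.
- *Cohort 4-5 TL2s are unselected.* They are not selected on necrosis, but protocol 10.2 and SAP 5.9 end dosing after a TRAE SI (protocol 7.3.1 leaves a Part 2 TRAE SI to the medical monitor). Some selection on tolerability remains.

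**Conclusion.** The selection is built into the dosing rule, and the SAP does not account for it. The treated-TL2 rows for Part 1 and Cohorts 1-2 in 8.1, 8.2 and 8.6 are conditional on an early visual response in TL1, and the Part 2 Total TL2 row pools them with TL2s that are not. For 8.3 and 8.5 the narrower conclusion is that the TL2 population is undefined.

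The size rests on assumed p, q and r. At p = 0.5 and r between 0.2 and 0.5, the selected rows carry 10 to 25 points at q = 0.5 and 5 to 12.5 at q = 0.8; there is no bias if lesions respond independently. At q = 0.5 and an even spread of second lesions the Part 2 Total moves by 0.6 to 1.5 points, which would not change its reading. The main risk is that TL2 results from at most 19 subjects (10 + 6 + 3) are read as independent confirmation. Minor.

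**What to change.** - In SAP 8.1, 8.2, 8.3 and 8.5, add the Displayed Total over Cohorts 4 and 5 that 8.6 already uses. Apply it to all lesion rows, so that the column has one population, and base any pooled TL2 efficacy statement on it. Removing Cohorts 1-2 from the TL2 row of the Part 2 Total alone would leave that column with different populations for TL1 and TL2.
- In 8.3 and 8.5, limit the TL2 target-lesion rows to treated TL2s. Uninjected ones remain visible in the listings of all lesions under 8.1 and 8.2.
- Footnote the TL2 rows of Part 1, Cohort 1 and Cohort 2 as treated only after TL1 necrosis, and base efficacy statements for those groups on TL1.

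The cost is SAP wording, one more total column, and a few lesions left out of the pooled TL2 figure. Data collection and dosing are unchanged. If the database is already locked, SAP 5.2 requires the additions to be labelled post hoc.

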## **Cohort 4 expansion group:**

An SRC meeting was convened after the 10 subjects in Cohort 4 completed the Safety Assessment and approved the following:

- Up to 20 additional subjects (for a total of approximately 30 subjects) will be enrolled into Cohort 4.
- After each treatment, the additional subjects enrolled into Cohort 4 expansion: will remain in the study center for up to 1-hour (reduced from 2-hours) post second injection for safety monitoring (e.g., continuousblood pressure, electrocardiographic and AE monitoring), an additional hour may be continued at the discretion of the PI.

# **Cohort 5 expansion group:**

An SRC meeting was convened after the 10 subjects in Cohort 5 completed the Safety Assessment and approved the following:

- Up to 20 additional subjects (for a total of approximately 30 subjects) will be enrolled into Cohort 5.
- After each treatment, the additional subjects enrolled into Cohort 5 expansion: will remain in the study center for up to 1-hour (reduced from 2-hours) post second injection for safety monitoring (e.g., continuous blood pressure, electrocardiographic and AE monitoring), an additional hour may be continued at the discretion of the PI.

Plasma PK sampling will be collected in subjects in Cohorts 4 and 5 expansion groups as detailed in Table 8-1.

**Planned Sample Size:** Approximately 80 subjects (Part 1: approximately 2 to 8 subjects; Part 2: approximately 66 to 72 subjects enrolled at up to 15 sites in the United States (US).

13October 2023

**Duration of Treatment:** The Sponsor estimates that the study will require approximately 17 months from the time that the first subject provides signed informed consent through the last subject's last study-related visit (up to 42 days Screening; treatment in 1-week intervals until visual confirmation of necrosis of target lesions; surgical excision of all target and nontarget lesions 4 to 6 weeks (Part 1) and 12 to 14 weeks after W1D1 injection; follow-up (F/U) visit at 1- or 2-weeks post excision).

Duration of participation for an individual subject will depend on assessments of disease and tolerability of VP-315, as well as other factors. No subject will be treated for more than 2 weeks. All lesions will be excised 4 to 6 weeks (Part 1) and 12 to 14 weeks (Part 2) after the W1D1 injection.

Key Subject Eligibility Criteria: Screening: Adults  $\geq 18$  years of age who have clinically suspected low-risk BCC with at least 1 eligible lesion suitable for biopsy and excision. Additionally, to be eligible for participation in the study, subjects are required to have a histological diagnosis of BCC in at least 1 eligible target lesion (confirmed by punch or shave biopsy) that is suitable for biopsy and excision; all lesion(s) enrolled in the study (target and non-target) must be  $\geq 0.5$  cm, and  $\leq 2.0$  cm in the longest diameter, may not be recurrent or previously treated, and must not be within 1 cm of the eyelids or lips, or on the hands, ears, nose, or genitalia.

Test Product, Dose, and Route of Administration: VP-315 comprises a de novo designed oncolytic peptide provided as LTX-315 Acetate 20 mg/vial lyophilized powder for injection that can be reconstituted in saline to a concentration ranging from 4 to 16 mg/mL. VP-315 will be administered via intradermal injection into a single target lesion. In all parts of the study, the targeted total volume of delivery is 500  $\mu$ L daily. In Part 1, the 500-uL dose will be divided into 2 injections given at least 15 minutes and no more than 30 minutes apart, with 30% (150  $\mu$ L) administered in the first injection and the remaining 70% (350  $\mu$ L) with the second injection. Part 2 (Cohorts 1 and 2) will determine the optimal dosing regimen for an 8mg dose based on safety, tolerability, and biological response to VP-315. This optimal dosing regimen will be used in Part 2 (Cohorts 4 and 5).

Reference Product, Dose, and Route of Administration: None.

**Statistical Considerations**: No formal inferential statistical analyses will be performed. Data will be summarized using descriptive statistics (number of subjects, mean, median, standard deviation, minimum, and maximum) for continuous variables and using frequency and percentage for discrete variables. Results will be presented by study period. Data will be presented for all subjects in listings.

An accounting of the study subjects by disposition will be tabulated. Demographic data (e.g., age, gender, and race), medical history, cancer history, and other baseline characteristics will be summarized.

Safety Evaluation: The general safety and tolerability of VP-315 will be assessed using the following safety endpoints: AEs, DLTs (Part1), TRAE SIs (Part 2), CRAs, routine clinical laboratory evaluations (serum chemistry, hematology), serum tryptase levels, vital signs, electrocardiograms (ECGs) and physical examination. The incidence (%) of all treatment emergent adverse events (TEAEs) will be summarized by body system and preferred term.

13October 2023

Incidence rates of TEAEs will also be presented by severity and relatedness to study medication. Changes from baseline in vital signs, ECGs and laboratory values will be summarized.

Efficacy Evaluation: Efficacy will be assessed using the following efficacy endpoints: clinical clearance, histological clearance, complete clearance, tumor volume estimate, abscopal effect, and Physician's Global Assessment. The number and percentage of lesions in each category will be tabulated overall. The number and percent of lesions that achieve histological clearance will be displayed. The same analysis will be repeated for the number of lesions that achieve clinical clearance. Tumor volume estimates will be summarized using descriptive statistics.

Exploratory Evaluation: In Part 2 of the study, the immune response to VP-315 treatment will be evaluated in a subset of subjects. Tumor tissue samples from the pre-treatment screening biopsies and from the post-treatment excised tumor tissue will undergo multiplexed IF-IHC and changes in the expression of a panel of 8 immune markers in response to the treatment will be analyzed. Additionally, genomic DNA will be isolated from the same tissue samples, as well as well as from peripheral blood samples collected at the same pre- and post-treatment time points and will undergo sequencing and analyzed for changes in T-cell receptor clonality.

